4.1.1 Inclusion Criteria

Patients must meet the following criteria for study entry:

- Adult patients: Signed informed consent by any patient capable of giving consent, or, where the patient is not capable of giving consent, by his or her legal/authorized representative
- Adolescent patients not able to legally consent: written informed consent for study participation is obtained from patient’s parents or legal guardian, with assent as appropriate by the patient, depending on the patient’s level of understanding and capability to provide assent
- Age \geq 12 years at the time of signing the Informed Consent Form/Assent Form
- Ability to comply with the study protocol, in the investigator’s judgment
- Patients who require hospitalization for severe influenza or acquire influenza during hospitalization, the severity of which requires an extension of hospitalization
- Diagnosis of influenza A and/or B by a positive Rapid Influenza Diagnostic Test (RIDT) or reverse transcriptase-polymerase chain reaction (RT-PCR)

Positive results from local tests are acceptable if conducted within the 24 hours prior to screening.

A patient with a negative RIDT may be enrolled if influenza is suspected based on local surveillance data or if the patient reports contact with a known case of influenza within the prior 7 days and all other inclusion criteria are met

- The time interval between the onset of symptoms and randomization is within 96 hours

The onset of symptoms is defined as the time when the patient experiences at least one new general symptom (e.g., headache, feverishness or chills, muscle or joint pain, fatigue), respiratory symptom (e.g., cough, sore throat, nasal congestion), or fever.

- A score of ≥ 4 based on the NEWS2 (see [Appendix 3](#))
- Patients will require objective criteria of seriousness defined by at least one of the following criteria:
 - Requires ventilation or supplemental oxygen to support respiration
 - Has a complication related to influenza that requires hospitalization (e.g., pneumonia, CNS involvement, myositis, rhabdomyolysis, acute exacerbation of chronic kidney disease, asthma or chronic obstructive pulmonary disease [COPD], severe dehydration, myocarditis, pericarditis, exacerbation of ischemic heart disease)
- For women of childbearing potential: Agreement to remain abstinent (refrain from heterosexual intercourse):

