6.1 DETERMINATION OF SAMPLE SIZE

Two new factors influenced the revised sample size: 1) the revised assumption for the placebo plus NAI control-arm TTCI following blinded data review (Section 6.1.1) and 2) the faster than anticipated enrollment rate. Integration of these two factors informed a sample size readjustment to approximately 366 randomized patients. Assuming that the RT-PCR-positive rate (tested in a central laboratory) will be 75% of the randomized population and a dropout rate of 4%, the modified intent-to-treat (influenza) infected (mITTI) population will be 264 patients (i.e., 176 patients in the baloxavir marboxil group and 88 in the placebo group). The total number of randomized patients may change based on the percentage of patients who are RT-PCR positive during the study.

The total mITTI sample size of 264 patients provides at least 80% power using the Logrank Chi-Square test to detect a 31-hour difference in TTCI between treatment groups under the following assumptions: median TTCI in the placebo plus NAI group is 94 hours, 840 hours follow-up (35 days) using 5% alpha. The minimal detectable difference is expected to be around 23 hours. The alteration of the TTCI in the placebo plus NAI group to 94 hours was selected after consideration of the response rates observed in a blinded review (see Section 6.1.1) of TTCI including data from 127 patients.

The increased sample size has the consequential benefit of a larger population for safety analysis of the combination and multiple dose regimen specifically tested in this study for the severely ill hospitalized patient group.

The study power is calculated based on the primary endpoint incorporating a group sequential design (GSD) using a beta spending function with non-binding rule, to allow for one futility interim, without increasing the overall experiment-wise error rate.

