6.4.1 Primary Efficacy Endpoint

The primary efficacy objective for this study is to evaluate the efficacy of baloxavir marboxil plus a SOC NAI, compared with matching placebo plus SOC NAI on the basis of the following endpoint:

- TTCI (defined as time to hospital discharge or time to NEWS2 of ≤ 2 and maintained for 24 hours, whichever comes first)

The median TTCI will be compared between the baloxavir marboxil plus SOC NAI and matching placebo plus SOC NAI arms using the stratified log-rank test within three regions (*i.e.*, North America, EMEA, ROW), NEWS2 (≤ 7 , > 7), and time from symptom onset to study treatment (≤ 48 hours, > 48 hours) included as the stratification factors. The Kaplan-Meier plot, median time to response, 95% CIs, and p-values will be presented.

The log-rank test requires the assumption of proportional hazards to be met. The proportional hazards assumption will be tested graphically using the log cumulative hazard plot by treatment group. The plots for each treatment group will be parallel if the

proportional hazard assumption holds. *Using a Cox model, the slope of a linear regression will also be tested and a plot of scaled Schoenfeld residuals against the Kaplan-Meier estimator investigated.*

Should the proportional hazards assumption be violated, the Gehan-Wilcoxon test will be used to analyze the data *as the logrank test can be under powered in this situation.* All investigations will be detailed in the statistical section of the CSR.

The estimand is the median change in TTCI. This absolute measure will be assessed over the duration of the study (35 days). Intercurrent events are those that occur after treatment initiation and either preclude observation of the variable or affect its interpretation. Intercurrent events will be accounted for through censoring rules. Patients who are lost to follow-up, who do not have a clinical response event, who die or discontinue for any reason prior to achieving a clinical response event will be censored at their last contact date or date of death, whichever is applicable. No dose reductions or treatment cross-overs are anticipated.

As specified in Section 6.4, the primary efficacy analysis population will be the modified-ITTI population, which consists of all patients who were randomized to treatment, received a dose of study drug, and were RT-PCR positive for influenza *at any timepoint.*

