Appendix 3 National Early Warnig Score 2 (NEWS2) (cont.)

For physiological parameter “Air or Oxygen?”: Any patients requiring the use of oxygen or other forms of ventilation to maintain oxygen saturations and support respiration should be assigned a score of 2.

The consciousness level should be recorded according to the best clinical condition of the patient during the assessment. Patients who are assessed as “Alert” (A) should be assigned a score of 0. Patients assessed as “New Confusion” (C), “Responsive to Voice” (V), “Responsive to Pain” (P), or “Unconscious” should be assigned a score of 3.

Scores should be assigned for respiratory rate, systolic blood pressure, pulse, and temperature according to the table above.

The NEWS2 should be recorded in the eCRF at the screening visit to ensure patients meet the eligibility criteria. In addition to the total NEWS2, the individual components of the score should also be recorded in the eCRF. Additional NEWS2 values will be calculated electronically throughout the study by the Sponsor based upon entry of vital sign parameters by the investigator in the appropriate eCRF.

Example Case Calculation:

A 82-old lady was admitted to an acute medical unit from a residential care home. Her taken observations and corresponding NEWS2 score are as follows:

Physiological Parameter	Observation	Component Score
Respiratory rate (per min)	26	3
Oxygen saturations (SpO ₂ %)	95%	1
Supplemental Oxygen	No	0
Systolic blood pressure (mmHg)	140	0
Pulse Rate (bpm)	109	1
Conscious level	Alert	0
Temperature (°C)	39	1
	Total NEWS2 Score	6

Appendix 4

Management Criteria for Abnormal Liver Function Tests

Management Criteria for Abnormal Liver Function tests have been designed to ensure patient safety and evaluate liver event etiology (see Guidance for Industry Drug-Induced Liver Injury: Premarketing Clinical Evaluation, FDA: 2009; available from: <https://www.fda.gov/downloads/Guidances/UCM174090.pdf>).

Abnormal Liver Chemistry Criteria

The investigator or subinvestigator must review study patient laboratories to identify if any levels meet the following criteria:

- AST or ALT $> 5 \times$ upper limit of normal (ULN)
- AST or ALT $> 3 \times$ ULN and total bilirubin (TBL) $> 2 \times$ ULN or INR > 1.5 , if INR is measured

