4.5 EFFICACY ANALYSIS

Efficacy analyses will be conducted for the mITTI population. Hypothesis tests will be two-sided at the 5% significance level, unless stated otherwise.

To manage the overall type I error, the primary and key secondary endpoints will be tested sequentially. The order of testing will be as follows:

- TTCl
- Response rates of the 6-point ordinal scale at Day 7
- Time to Clinical Response

If the primary efficacy analysis hypothesis test result is not statistically significant (i.e. $p > 0.05$), the hypothesis below that result in the hierarchical chain will be considered exploratory and no claims of statistical significance will be made. The same rules apply to the next endpoint in the chain.

4.5.1 **Primary Efficacy Endpoint**

The primary efficacy objective for this study is to evaluate the efficacy of baloxavir marboxil plus a SOC NAI, compared with matching placebo plus SOC NAI based on the following endpoint:

- TTCI (defined as time from treatment start to hospital discharge or time to NEWS2 ≤ 2 and maintained for 24 hours, whichever comes first)

TTCI is calculated as per [Table 3](#).

Table 3 TTCI Calculations

TTCI based on	TTCI (hours)
NEWS2 ≤ 2 for 24 hours	date time of initial NEWS2 assessment ≤ 2 - start treatment date time
NEWS2 ≤ 2 prior to discharge*	date time of initial NEWS2 assessment ≤ 2 - start treatment date time
Hospital discharge	date time of hospital discharge - start date time of treatment

*when a patient met the NEWS2 ≤ 2 and was discharged from hospital during the 24 hour period of stability confirmation, the time of achieving TTCI was defined as the initial time at which the NEWS2 ≤ 2 and not the time of hospital discharge.

NEWS2 (National early warning score 2) is the sum of the score of each of the following assessments, as described in [Appendix 4](#): respiration rate (per minute), oxygen saturation (SpO₂%) according to scale 1 or scale 2, supplemental oxygen or room air, systolic blood pressure (mmHg), pulse rate (bpm), consciousness level, temperature (°C).

Missing data for the calculation of the NEWS2 will not be imputed for the following reasons:

1. TTCI endpoint can be met through hospital discharge.
2. The physiological components of the NEWS2 can be highly heterogeneous in the study patient population and therefore the process of imputation would not be relevant.

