The TTCI will be compared between the baloxavir marboxil plus SOC NAI and matching placebo plus SOC NAI arms using the stratified log-rank test within three regions (i.e. North America, EMEA, ROW), NEWS2 score at baseline (≤ 7 , > 7), and time from symptom onset to study treatment (≤ 48 hours, > 48 hours) included as the stratification factors. The Kaplan Meier plot, median time to response, 95% CIs, and p-values will be presented.

The log-rank test is most appropriate when the assumption of proportional hazards is met. The proportional hazards assumption will be tested graphically using the log cumulative hazard plot by treatment group. The plots for each treatment group will be parallel if the proportional hazard assumption holds. Should the proportional hazards assumption be violated, the Gehan Wilcoxon test will be used to analyze the data.

The estimand is the difference in distributions between baloxavir marboxil plus SOC NAI and matching placebo plus SOC NAI arms in the mTTi for the TTCI using appropriate method, as described above. This absolute measure will be assessed over the duration of the study (35 days). The median TTCI for each treatment group and difference between treatment groups will be presented. Intercurrent events are those that occur after treatment initiation and either preclude observation of the variable or affect its interpretation. Intercurrent events, such as patients who are lost to follow-up, die or discontinue for any reason prior to achieving a clinical improvement or do not have a clinical improvement event, will be accounted for through censoring rules, as described in [Table 4](#) below.

Table 4 TTCI and Censoring

Event	Censor	Date and Time
Clinical improvement (based on NEWS2 \leq 2 for 24 hours)	No	vital signs assessment where NEWS2 \leq 2 at start of 24 hour period
Clinical improvement (based on NEWS2 \leq 2 prior to discharge)	No	first vital signs assessment where NEWS2 \leq 2 prior to discharge
Clinical improvement (based on hospital discharge)		
- hospital discharge and hospital re-admission within 24 hours) and discontinue study on same day	Yes	hospital discharge
- hospital discharge and hospital re-admission within 24 hours) and continue study	Yes	hospital discharge
- hospital discharge against medical advice (i.e. self-discharge)	Yes	hospital discharge
- all other hospital discharge	No	hospital discharge
Death prior to achieving a clinical improvement	Yes	last vital signs assessment prior to death

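### The primary TTCI test uses baseline NEWS2 only through the cut at 7; adding the total score already collected could recover a few points of power

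*SAP*

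**What the plan says.** Protocol 6.4.1 compares the "matching placebo plus SOC NAI arms using the stratified log-rank test". SAP 4.5.1 repeats this, "using the stratified log-rank test within three regions (i.e. North America, EMEA, ROW), NEWS2 score at baseline" in two categories (7 or below, above 7) and time from symptom onset (48 hours or less, more than 48 hours). These are the randomisation factors of Protocol 4.2 and SAP 3.1, and they give 3 × 2 × 2 = 12 strata.

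The SAP defines TTCI as "time from treatment start to hospital discharge or time to NEWS2" of 2 or below kept for 24 hours, whichever comes first. Protocol 4.1.1 requires "A score of ≥ 4 based on the NEWS2" for entry. On data capture, Protocol Appendix 3 states: "The NEWS2 should be recorded in the eCRF at the screening visit to ensure patients meet the eligibility criteria". It asks for the total and the component scores.

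No planned TTCI analysis uses NEWS2 on a finer scale. The subgroups in SAP 4.5.4 use the same cut. The only covariate adjustment, in SAP 4.5.1.1, is a sensitivity analysis for imbalances linked to reasons for discontinuation, and it does not name NEWS2. For change in viral titre and viral RNA, by contrast, SAP 4.6 fits an ANCOVA with the strata and the baseline value of the measure as a covariate.

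**The concern.** Within the lower NEWS2 stratum, a patient who enters at 4 must fall 2 points to reach the threshold, and a patient who enters at 7 must fall 5. If the score predicts time to improvement within the categories, the planned test leaves that variation in the comparison. The estimated effect is then diluted, and a chance imbalance in severity inside a stratum goes unadjusted.

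TTCI opens the testing hierarchy, so a missed primary result also closes off both key secondary endpoints. The design has little slack: the working below finds 262 events needed against 264 patients planned. A baseline value that is already collected is a cheap source of power, and the SAP already applies the principle to its virology endpoints.

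**Working it through.** **Inputs from the documents.** Control median 94 h, difference 31 h (so 63 h on baloxavir), 840 h follow-up, 264 mITTI patients split 176 and 88, 75% RT-PCR positive, 4% dropout (Protocol 6.1). Two-sided 5% tests (SAP 4.5: "Hypothesis tests will be two-sided at the 5% significance level, unless stated otherwise"). One non-binding futility look at about 65% of events with Pocock-type beta spending and a bound near p = 0.077 (SAP 2.5.1).

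**Step 1: reproduce the plan's figure.** Protocol 6.1 says the sample "provides at least 80% power using the Logrank Chi-Square test to detect a 31-hour difference".
- Exponential times: HR = 63/94 = 0.670, |ln HR| = 0.4002. About 263.8 of the 264 patients have the event by 840 h.
- Fixed design (Schoenfeld, 2:1): drift = 0.4002 × √(264 × 2/9) = 0.4002 × 7.659 = 3.065. Power = Φ(3.065 − 1.960) = 86.5%.
- With the futility look: beta spent at 65% = 0.20 × ln(1 + (e − 1) × 0.65) = 0.150. The drift needed for 80% power is 3.052, so events needed = 3.052² / (0.4002² × 2/9) = 261.8. Power at 264 is 80.3%.
- Bound: z = 3.052 × √0.65 − 1.036 = 1.424, one-sided p = 0.077, as in the SAP.
- Randomised: 264 / (0.75 × 0.96) = 366.7, against about 366 stated.

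The stated design reproduces, by an unstratified calculation that does not rely on NEWS2 adjustment.

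**Step 2: what the cut pools.** Entry scores of 7 or below are 4, 5, 6 and 7. The falls needed to reach 2 are 2, 3, 4 and 5 points.

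**Step 3: power with and without linear NEWS2.** The NEWS2 distribution and its prognostic effect are assumptions. The simulation used 264 patients, 2:1 permuted blocks in 12 strata, exponential times with marginal medians of 94 and 63 h, censoring at 840 h, no interim, and 8,000 trials per scenario (Monte Carlo standard error about 0.45 points). Scores ran from 4 to 13, with 67% at 7 or below. The median ratio for score 7 against 4 is HR⁻³.

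| HR for improvement per NEWS2 point | Median ratio, 7 v 4 | Planned 12-stratum log-rank | Same strata + linear NEWS2 (Cox) | Difference (points) |
|---|---|---|---|---|
| 1.00 | 1.00 | 80.4% | 80.2% | −0.2 |
| 0.95 | 1.17 | 80.6% | 80.3% | −0.3 |
| 0.90 | 1.37 | 79.5% | 80.5% | +1.0 |
| 0.85 | 1.63 | 77.7% | 79.6% | +1.9 |
| 0.80 | 1.95 | 75.4% | 79.7% | +4.3 |

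With 50% at 7 or below, the differences are −0.1, 0.0, +1.0, +2.5 and +4.7 points.

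Only the differences answer the question. The levels near 80% are not the plan's 80%: they carry no futility look, and they include a loss from splitting into 12 cells. In the first row the unstratified log-rank gives 85.0%, so that loss is 85.0 − 80.4 = 4.6 points under the assumed stratum sizes.

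**Step 4: other assumptions.**
- Mean score 6.4, 28% above 7 (2,500 trials): 81.0% v 80.6% at 1.00, 81.3% v 82.4% at 0.90, 79.2% v 81.0% at 0.86, 77.9% v 80.8% at 0.82, 73.0% v 79.4% at 0.74. Type I error was 5.9% v 5.8%, with Monte Carlo error about 0.5 points.
- A further set of 2,000 trials: 80.4% v 80.6% at 1.00, 79.5% v 80.1% at 0.90, 78.9% v 80.4% at 0.82, 74.7% v 80.0% at 0.74. Type I error was 5.0% v 5.3%.
- Discharge unrelated to NEWS2 (4,000 trials, mean score 6.7, 32% above 7): at 0.82 the comparison is 76.7% v 79.8%. If 30% of the improvement hazard at the average score does not depend on NEWS2, it becomes 79.2% v 80.5% at 0.82, and 78.4% v 81.2% at 0.75.
- Non-linear effect (3,000 trials): −0.2 points if risk changes only at the cut, +0.4 if it is flat to 7 and then 0.82 per point, +1.0 if it is 0.82 per point to 7 and then flat.
- Finer NEWS2 strata (4–5, 6–7, 8–9, 10 or more): 74 to 76% in every scenario of Step 3, so no better than the planned test and mostly worse.

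**The case against.** The strongest reply is that nothing here is wrong. The test is stratified by exactly the factors used at randomisation, so it already adjusts for baseline NEWS2 at the chosen cut. Type I error is unaffected, and the sample size calculation does not depend on finer adjustment. All of this stands.

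A reader might infer that power is definitely lost, or that the baseline score is mostly thrown away. The documents support neither. They give no prognostic effect per point. Under one assumed distribution (mean 6.45, 28% above 7) the single cut already captures about 71% of the variance in NEWS2. Discharge also produces the event, which should weaken the link between entry score and TTCI. The largest figures need a strong effect: at 0.74 per point, a patient at 7 recovers 0.74⁻³ = 2.5 times more slowly than one at 4, and a patient at 13 about 0.74⁻⁹ = 15 times more slowly.

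The linear simulations also favour a linear model. NEWS2 moves in jumps (2 points for oxygen, 3 for altered consciousness), and the gain shrinks to between −0.2 and +1.0 points under the non-linear shapes tried.

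The discharge argument weakens the point but does not remove it. SAP Table 3 times a patient discharged during the 24-hour confirmation at the first NEWS2 of 2 or below, and Protocol 3.3.4 regards that score as potential readiness for discharge. With 30% of the hazard unrelated to NEWS2, a gain of 1.3 points (0.82) to 2.8 points (0.75) remained.

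**Conclusion.** The primary test forgoes information that is already collected, and using it is a worthwhile improvement. It is not a correction: the planned test is valid and its stated power reproduces.

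The power forgone is about 0 to 1 point if each NEWS2 point lowers the recovery hazard by up to 10%, about 1 to 3 points at 15 to 18%, and about 4 to 6 points at 20 to 26%. If NEWS2 is not prognostic within the categories, adjustment costs essentially nothing. These sizes rest on assumed score distributions, exponential times and a log-linear effect. A real effect that is far from linear, or discharge driven largely by other factors, would put the gain towards the lower end.

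It would go too far to conclude that the trial is underpowered because of the cut, or that its primary result would be unreliable.

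**What to change.** Before unblinding, pre-specify in SAP 4.5.1 a Cox model for TTCI with the existing randomisation strata and baseline NEWS2 as a linear covariate. Define baseline as the last total score before randomisation. Report the hazard ratio for treatment and its 95% CI.

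- **Preferred:** make the treatment term of this model the primary test and keep the stratified log-rank test as a sensitivity analysis. State in SAP 2.5.1 that the interim futility p-value uses the same test, and that the Gehan-Wilcoxon fallback is unchanged if proportional hazards fails. Record the departure from Protocol 6.4.1 in SAP 3.3.
- **Otherwise:** leave the primary test as it is and add the model as a named supportive analysis.

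Do not refine the NEWS2 strata.

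The cost is wording; no new data are needed. The preferred route also touches the interim text and the protocol's named primary test, so it is more than a one-line edit. The hazard ratio becomes conditional on NEWS2, and one linear term is assumed.

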3.3.4 Rationale for Endpoints

There is no validated clinical end-point for assessing improvement in patients hospitalized due to influenza. Consequently, *three* measures of clinical improvement are used in this study: “*time to clinical improvement*” as the primary endpoint, “*response rates of the 6-point ordinal scale*” and “*time to clinical response*” as *key secondary endpoints*. *The primary and both key secondary endpoints will be tested in a hierarchical chain to control the experiment-wise error rate (alpha).*

The primary endpoint for this study will be the time to clinical improvement (TTCI), defined as time to hospital discharge or time to National Early Warning Score 2 (NEWS2) of ≤ 2 maintained for 24 hours, whichever occurs first. This endpoint will provide objective evidence of improvement in a patient’s condition, which is likely to be a reasonable surrogate to overall clinical status improvement.

The original NEWS was created in the United Kingdom by the Royal College of Physicians in 2012 to standardize the process of recording, scoring, and responding to changes in routinely measured physiological parameters in acutely ill patients. The score has been widely implemented across the National Health Service in the United Kingdom, and in other healthcare settings across the world. NEWS2 is a similar but updated score (Royal College of Physicians 2017) to incorporate an additional oxygen scale for patients at risk of hypercapnic respiratory failure (target oxygen saturation of 88%–92%, rather than the standard target of $\leq 96\%$).

Six physiological parameters are routinely recorded:

- Respiration rate
- Oxygen saturation
- Systolic blood pressure
- Pulse rate
- Level of consciousness and new confusion (ACVPU: A=alert, C=new confusion, V=responsive to voice, P=responsive to pain, U=unconscious)
- Temperature

In addition, a weighting score of 2 is added for patients requiring supplemental oxygen to maintain their prescribed oxygen saturation range.

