3.3 DEVIATIONS FROM PROTOCOL

Since the finalization of the Protocol v2.0, the following updates have been made to the planned analysis:

Planned Interim Analysis

The statistic used to determine futility in the planned interim analysis per Protocol v2.0 was the hazard ratio:

- If the hazard ratio seen at the interim is below the calculated futility bound, the trial may be declared futile and recruitment will be stopped.

This has been updated to the p-value, to ensure consistency between the proportional hazards and non-proportional hazards scenarios in the analysis:

- If the p-value seen at the interim is above the calculated futility bound, the trial may be declared futile and recruitment will be stopped.

Clinical Response Definition

Clinical Response is defined per protocol as:

- For patients who achieve four of the five vital sign resolution criteria, both the temperature and oxygen saturation response criteria must be maintained for 24 hours for the clinical response endpoint to be met or hospital discharge, whichever occurs first.

This has been updated to:

- Clinical response is defined as resolution of at least 4 of the 5 vital signs within the respective resolution criteria, maintained for at least 24 hours, or hospital discharge, whichever occurs first.

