Event	Censor	Date and Time
Clinical Response (based on vital signs assessments)	No	first vital signs assessment where 4 out of 5 criteria initially met and subsequently maintained for 24 hours period
Clinical Response (based on vital signs criteria met prior to discharge)	No	first vital signs assessment where 4 out of 5 criteria initially met and maintained prior to discharge
Clinical Response (based on hospital discharge)		
- hospital discharge to another hospital (i.e. hospital admission within 24 hours) and discontinue study on same day	Yes	hospital discharge
- hospital discharge to another hospital (i.e. hospital admission within 24 hours) and continue study	Yes	hospital discharge
- hospital discharge against medical advice	Yes	hospital discharge
- all other hospital discharge	No	hospital discharge
Death prior to achieving a clinical response	Yes	last vital signs assessment prior to death
Discontinuation for any reason prior to achieving a clinical response	Yes	last vital signs assessment prior to discontinuation
Lost to follow-up	Yes	last vital signs assessment
No clinical response	Yes	last vital signs assessment

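### SAP Tables 4 and 11 date an event to the first NEWS2 ≤2 reading before discharge with no 24-hour or maintenance condition, contradicting the Table 3 footnote, the protocol's TTCI and Table 11's own definition

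*SAP*

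**What the plan says.** **Protocol.** Sections 3.3.4 and 6.4.1 define TTCI as hospital discharge or NEWS2 ≤2 "maintained for 24 hours, whichever occurs first". A patient who leaves before 24 hours of stability are complete therefore has the event at discharge.

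**SAP 4.5.1, Table 3.** The text makes this table the calculation rule for TTCI. One row covers NEWS2 ≤2 before discharge. Its footnote applies when the patient "was discharged from hospital during the 24 hour period of stability confirmation". The event time then "was defined as the initial time at which the NEWS2" criterion was met "and not the time of hospital discharge".

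**SAP 4.5.1, Table 4.** The matching row is uncensored and timed at the "first vital signs assessment where NEWS2 \leq 2 prior to discharge". It carries no footnote, no time limit and no maintenance condition. Further down, discharge with readmission within 24 hours and discharge against medical advice are both censored at discharge.

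**SAP 4.5.2.3, Table 7 (time to clinical response).** The parallel row does carry the condition: "first vital signs assessment where 4 out of 5 criteria initially met and maintained prior to discharge".

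**SAP 4.5.3, Table 11 (time to NEWS2 ≤2 maintained for 24 hours).** The definition requires 24 hours of maintenance and has no discharge component. The table nevertheless repeats the Table 4 row as an uncensored event, without a footnote. Its last row censors patients who did not achieve 24 hours.

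**SAP 3.3.** Under "Since the finalization of the Protocol v2.0, the following updates have been made to the planned analysis" it lists two changes: the interim futility statistic and the clinical response definition. Backdating of TTCI is not listed.

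**The concern.** NEWS2 is recorded four times a day in hospital up to Day 10 (Protocol 4.5.4), so isolated low readings followed by a rise are possible. A programmer working from Table 4 could time such a patient at the isolated reading. One working from Table 3 would use discharge. Because an external group runs the futility analysis on TTCI (SAP 2.5.1), the interim and final derivations could also differ.

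Three things are at stake:

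- **Event time in the primary analysis.** The 94-hour planning median came from a blinded evaluation of the protocol-defined TTCI (Protocol 6.1.1). A different timing rule breaks that link.
- **Event status in the primary analysis.** This affects patients who fit both row 2 and a censoring row of Table 4.
- **Event status in Table 11.** Here row 2 creates events that the definition excludes.

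**Working it through.** **1. The plan's own power figure.** Inputs from SAP 2.4 and 2.5.1: 366 randomized, 75% RT-PCR positive, 4% dropout, 176:88, medians 94 and 94 − 31 = 63 h, 840 h follow-up, two-sided 5%, one futility look at 65% of events. Exponential times are assumed.

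- mITTI: 366 × 0.75 × 0.96 = 263.5.
- Hazard ratio (control to active): 63/94 = 0.670.
- Events: 176 × (1 − 2^(−840/63)) + 88 × (1 − 2^(−840/94)) = 263.8.
- Drift: √(263.8 × 1/3 × 2/3) × |ln 0.670| = 3.064.
- Power without an interim: Φ(3.064 − 1.960) = 86.5%.
- Beta spent at 65%: 0.2 × ln(1 + (e − 1) × 0.65) = 0.150.
- Bound: 3.064 × √0.65 − 1.036 = 1.434, one-sided p = 0.076 (the SAP gives about 0.077).
- P(Z1 > 1.434 and Z2 > 1.96) = 80.2%.

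The stated power of at least 80% reproduces and is not in question.

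**2. The rules applied to single patients.**

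| Case | Protocol | Table 3 with footnote | Table 4 as worded |
|---|---|---|---|
| A. ≤2 at 24 h, above 2 at 30 h, no stable 24 h, discharged 120 h | 120 h | 120 h | 24 h |
| B. ≤2 at 60 h, held, discharged 70 h | 70 h | 60 h | 60 h |
| C. As B, but a reading above 2 between 60 and 70 h | 70 h | unclear | 60 h |
| D. As B, but self-discharge at 70 h | self-discharge not addressed | not addressed | event at 60 h or censored at 70 h |

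In A, Table 4 is 120 − 24 = 96 h earlier than both other rules. In B the footnote moves the event by 10 h; by construction the move is always under 24 h. In C the phrase about stability confirmation suggests that the score must hold, but no sentence requires it.

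In Table 11, case B is an event at 60 h by row 2, fails the definition, and also fits the last row, which censors at the last vital signs assessment.

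**3. Trial-level size (illustrative).** The documents give no dip rate. It is assumed at 0 to 30% of patients, equal in both arms, with 4,000 log-rank simulations per cell, 176:88, no interim. Cells show difference in medians (h) / power (%).

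| Rule | 0% | 10% | 20% | 30% |
|---|---|---|---|---|
| Table 4 literal, dip uniform over time to event | 31.0 / 83.3 | 29.1 / 82.3 | 26.8 / 79.8 | 24.5 / 78.5 |
| Table 4 literal, dip at 6–48 h unrelated to treatment | 31.7 / 85.1 | 27.3 / 80.0 | 19.9 / 71.1 | 11.4 / 63.3 |
| Table 3 footnote, shift 0–24 h | 31.7 / 85.7 | 31.5 / 85.7 | 31.9 / 85.5 | 31.7 / 85.9 |

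The three 0% cells are the same scenario and range from 83.3 to 85.7%, so differences of about two points are noise. Under the footnote at 30%, both medians fall by about 3.3 h (94.9 to 91.6 and 63.2 to 59.9).

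A second simulation modelled a declining, noisy score with 6-hourly readings (assumed reading-to-reading SD 0.7 to 1.6; discharge on average 12 to 36 h after a latent score of 2.5). The median fell by about 11 to 13 h under the footnote and about 24 to 54 h under a literal Table 4. It did not compare arms. The size of the shift therefore depends heavily on the assumptions.

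**The case against.** The strongest reply is that Table 3 governs. SAP 4.5.1 names it as the calculation rule, Table 4 is introduced as the handling of intercurrent events, and its row reuses Table 3's label. On that reading the footnote carries over and case A is timed at discharge. This largely stands, and it rules out the inference that Table 3 also lets a patient who dips, relapses and leaves days later count at the dip. It does not settle the matter. No sentence gives Table 3 precedence, and SAP Table 15 sends the reader to Table 3 for TTCI censoring rules that are actually in Table 4.

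Second, dating a patient discharged mid-confirmation to the initial reading is coherent, because Table 3 dates sustained improvement to its first reading too. That stands as a choice. It still differs from the protocol and is undeclared.

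Third, a reader might set the shift of up to 24 h against the 31-hour target. Those are unlike quantities: one is a maximum for a single patient, the other a between-arm difference in medians. The same rule applies to both blinded arms, and nothing in the documents points to a bias favouring either.

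Fourth, the overlap of event and censoring rows is an ambiguity, not a stated wrong rule, and Table 7 has the same row structure. That is correct; the remedy is a precedence sentence. Table 11's endpoint is outside the testing hierarchy, which limits the consequence there.

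**Conclusion.** The point holds as a defect in Tables 4 and 11. As worded, row 2 of each dates an uncensored event to an isolated low reading. In Table 4 this contradicts the Table 3 footnote and the protocol, and for most affected patients it changes the event time only. For self-discharge and readmission within 24 hours it leaves event status undetermined. In Table 11 it changes event status against the endpoint's own definition.

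If the footnote is applied, the shift is under 24 h per patient, and the simulated between-arm difference and power barely move. The larger losses, down to a difference of about 24 h or 11 h at a 30% dip rate, need both a literal Table 4 and a dip rate and pattern that the documents do not supply. A reader might infer that TTCI has become time to first low reading, or that the stated power is wrong. The documents support neither: Table 3 limits the rule, and the power figure reproduces.

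**What to change.** - **Tables 3 and 4.** Apply the pre-discharge row only when discharge occurs within 24 hours of the reading and every recorded NEWS2 from that reading to discharge is ≤2. Otherwise the event time is discharge.
- **Precedence.** State that the self-discharge and readmission censoring rows override row 2. The same sentence would serve Table 7.
- **Table 11.** Either remove row 2, or restrict it in the same way and amend the SAP 4.5.3 definition to say that discharge during confirmation counts. Restricting the row without amending the definition would leave the conflict in place.
- **SAP 3.3.** List the backdating as a change from the protocol.
- **SAP 4.5.1.1.** Add a sensitivity analysis that times these patients at discharge. None of those listed does so.
- **SAP Table 15.** Correct the TTCI censoring reference to Table 4.

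The cost is SAP wording and a few lines of derivation code, with no new data. It should be settled before unblinding and shared with the group that runs the interim analysis. The downside is that reported medians may become slightly longer.
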